4.5.2. Secondary Efficacy Variables

The secondary efficacy variables include:

- Proportion of patients achieving EASI-50 ($\geq 50\%$ improvement from baseline) at week 16
- Proportion of patients achieving EASI-75 ($\geq 75\%$ improvement from baseline) at week 16
- Proportion of patients achieving EASI-90 ($\geq 90\%$ improvement from baseline) at week 16
- Absolute change in EASI score from baseline to week 16
- Proportion of patients with both an IGA score of 0 or 1 (on a 5-point scale) and a reduction from baseline of ≥ 2 points at week 16
- Change (absolute and percent) from baseline to week 16 in weekly average of daily peak Pruritus Numerical Rating Scale (NRS)
- Proportion of patients with improvement (reduction) of weekly average of daily peak Pruritus NRS ≥ 4 from baseline at week 16

Investigator's Global Assessment (IGA)

The IGA is a static 5-point assessment instrument to rate AD disease severity globally in clinical studies. The ratings (0 = clear, 1 = almost clear, 2 = mild, 3 = moderate, 4 = severe) are an overall assessment of AD skin lesions based on erythema and papulation/infiltration.

Pruritus Numeric Rating Scale (NRS)

The Pruritus NRS is a simple assessment tool that patients will use to report the intensity of their pruritus (itch) using an electronic questionnaire (e-diary).

At screening, patients will be instructed on using the e-diary to record the worst intensity of their itch/pruritus, using a scale from 0 to 10, where 0 is no itch and 10 is the worst itch imaginable. Patients will complete the rating scale twice every day, morning and evening reports, through the entire study (screening, treatment, and follow-up periods). Clinical sites will check patient data collected using an e-diary for protocol compliance and remind patients to complete their e-diary throughout the study.

The daily peak pruritus NRS score is the worse one between the morning and evening scores of the day.

The baseline Pruritus NRS score will be determined based on the average of daily NRS scores during the 7 days immediately preceding randomization (i.e. study day -7 to day -1). A minimum of 4 daily scores out the 7 days is required to calculate the baseline average score.

For post-baseline Pruritus NRS score, the weekly average is calculated as the prorated average of the reported daily NRS within the week. For example, if there are 3 scores in a week, the prorated average = (score1 + score2 + score3)/3.

The weekly worst score is calculated by taking the worst score within the week.

The endpoint "Proportion of patients with improvement (reduction) of peak daily Pruritus NRS ≥ 4 from baseline to week 16" will be based on the weekly average of daily peak Pruritus NRS score.

Body Surface Area (BSA) Involvement of Atopic Dermatitis

Body surface area affected by AD will be assessed for each section of the body (the possible highest score for each region is: head and neck [9%], anterior trunk [18%], back [18%], upper limbs [18%], lower limbs [36%], and genitals [1%]) and will be reported as the sum of all the percentages combined. .

4.5.3. Other Efficacy Variables

Other efficacy variables include:

- Change (absolute and percent) from baseline to week 16 in weekly average of daily Peak Pain NRS
- Change (absolute and percent) from baseline to week 16 in weekly average of daily Sleep Quality NRS

Peak Pain Numeric Rating Scale (NRS)

The Peak Pain NRS is a simple assessment tool that patients will use to report the intensity of their pain during a 24-hour recall period using an electronic questionnaire. Patients will be asked to answer the following question on a scale from 0 (no pain) to 10 (worst pain possible):

For the question below, think about all the areas of your skin with eczema.

“How would you rate your skin pain at its worst in the previous 24 hours?”

Patients will be instructed on using an electronic questionnaire to record their Peak Pain NRS score at the screening visit. Patients will complete the rating scale DAILY through the entire study (screening, treatment, and follow-up periods).

The daily peak pain NRS score and weekly average for post-baseline pain NRS score are calculated using the same algorithm for daily peak, and weekly average of pruritus NRS score.

Sleeping Quality Numeric Rating Scale (NRS)

The Sleep Quality NRS is a simple assessment tool that patients will use to report the quality of their sleep during a 24-hour recall period using an electronic questionnaire. Patients will be asked the following question on a scale of 0 (best possible sleep) to 10 (worst possible sleep) upon awakening for the day:

“Select the number that best describes the quality of your sleep last night.”

Patients will be instructed on using an electronic questionnaire to record their Sleep Quality NRS score at the screening visit. Patients will complete the rating scale DAILY through the entire study (screening, treatment, and follow-up periods).

The baseline sleeping quality NRS score will be determined based on the average of daily NRS scores during the 7 days immediately preceding randomization (i.e. study day -7 to day -1). A minimum of 4 daily scores out the 7 days is required to calculate the baseline average score.

For post-baseline sleeping quality NRS score, the weekly average is calculated as the prorated average of the reported daily NRS within the week. For example, if there are 3 scores in a week, the prorated average = (score1 + score2 + score3)/3.

4.6. Safety Variables

4.6.1. Adverse Events and Serious Adverse Events

Adverse events and serious adverse events will be collected from the time of informed consent signature and then at each visit until the end of the study. All adverse events are to be coded to a “Preferred Term (PT)”, “High Level Term (HLT)” and associated primary “System Organ Class (SOC)” according to the Medical Dictionary for Regulatory Activities (MedDRA) latest version available.

An **Adverse Event** is any untoward medical occurrence in a patient administered a study drug which may or may not have a causal relationship with the study drug. Therefore, an AE is any unfavorable and unintended sign (including abnormal laboratory finding), symptom, or disease which is temporally associated with the use of a study drug, whether or not considered related to the study drug.

AEs also include: any worsening (i.e. any clinically significant change in frequency and/or intensity) of a pre-existing condition that is temporally associated with the use of the study drug; abnormal laboratory findings considered by the investigator to be clinically significant; and any untoward medical occurrence.

The criteria for determining whether an abnormal laboratory, vital sign or ECG finding should be reported as an AE are as follows:

- Test result is associated with accompanying symptoms, and/or
- Test result requires additional diagnostic testing or medical/surgical intervention, and/or
- Test result leads to a change in dosing (outside of protocol-stipulated dose adjustments) or discontinuation from the study, significant additional concomitant drug treatment, or other therapy

A **Serious Adverse Event** is any untoward medical occurrence that at any dose results in death; is life-threatening; requires in-patient hospitalization or prolongation of existing hospitalization; results in persistent or significant disability/ incapacity; is a congenital anomaly/ birth defect; or is an important medical event.

The pre-treatment AEs are AEs that developed or worsened in severity during pre-treatment period defined as the period from the patient providing informed consent upto the first dose of study drug.

Treatment-emergent AEs (TEAEs) are AEs that developed or worsened in severity compared to the baseline during the treatment emergent period defined as the period from the administration of first study dose to the EOS visit. As only the worsening pre-existing AEs and new AEs reported during the treatment and follow-up period will be collected in the study, all AEs collected during the treatment and follow-up period are considered as TEAEs.

The skin infection TEAEs will be identified based on blinded adjudication of all reported TEAEs under the two primary system organ classes (SOCs): SOC = “Infection and infestations” or SOC = “Skin and subcutaneous tissue disorders”. Blinded adjudication will be done and finalized by the study medical monitor before database lock.

4.6.2. Adverse Events of Special Interest

In this study, the adverse event of special interest (AESI) category includes:

- Anaphylactic reactions or acute allergic reactions that require immediate treatment
- Severe ISRs that last longer than 24 hours
- Mycosis fungoides or other forms of cutaneous T-cell lymphoma
- Any severe infection; any infection requiring treatment with parenteral antibiotics/anti-viral/anti-fungal agent; any infection requiring treatment with oral antibiotic/anti-viral/anti-fungal for longer than 2 weeks; any clinical endoparasitosis; any opportunistic infection
- Conjunctivitis (any type or etiology), keratitis, or blepharitis (only events that are either severe or serious or lasting ≥ 4 weeks will be reported as AESIs)

- Significant ALT elevation
 - a. ALT >3×ULN associated with total bilirubin >2×ULN; or
 - b. ALT >5×ULN in patients with baseline ALT ≤2×ULN; or
 - c. ALT >8×ULN if baseline ALT >2×ULN

The search criteria for AESIs are provided in Section 10.4.

4.6.3. Laboratory Safety Variables

Hematology, chemistry, urinalysis, and pregnancy testing samples will be analyzed by a central laboratory.

Samples for laboratory testing will be collected according to visit schedule (Table 1). Tests will include

Serum Chemistry

Sodium	Total protein, serum	Total and indirect bilirubin
Potassium	Creatinine	Total cholesterol*
Chloride	Blood urea nitrogen (BUN)	Triglycerides
Carbon dioxide	AST	Uric acid
Calcium	ALT	CPK
Glucose	Alkaline phosphatase	
Albumin	Lactate dehydrogenase (LDH)	

* Low-density lipoprotein and high-density lipoprotein

Hematology

Hemoglobin	Differential:
Hematocrit	Neutrophils
Red blood cells (RBCs)	Lymphocytes
White blood cells (WBCs)	Monocytes
Red cell indices	Basophils
Platelet count	Eosinophils

Urinalysis

Color	Glucose	RBC
Clarity	Blood	Hyaline and other casts
pH	Bilirubin	Bacteria
Specific gravity	Leukocyte esterase	Epithelial cells
Ketones	Nitrite	Crystals
Protein	WBC	Yeast

Other Laboratory Tests

Serum and urine pregnancy testing will be performed for all female patients of childbearing potential at time points according to Table 1. The following tests will be performed at screening: HIV, HBsAg, HBsAb, HBcAb, hepatitis C antibody, and tuberculosis.

4.6.4. Vital Signs

The following vital signs parameters will be collected:

- Respiratory rate (bpm)
- Pulse (beats/min)
- Sitting systolic and diastolic blood pressures (mmHg)
- Body temperature (°C)

Vital signs (sitting blood pressure, pulse, and respiration rate) will be collected predose and 30 (± 10) minutes postdose. In addition, body temperature should be taken predose. See [Table 1](#) for assessment time points.

4.6.5. 12-Lead Electrocardiography (ECG)

Standard 12-Lead ECG parameters include: Ventricular HR, PR interval, QRS interval, corrected QT interval (QTc Fridericia [QTcF] = $QT/[RR^{0.33}]$ and QTc Bazett [QTcB] = $QT/[RR^{0.5}]$), ECG status: normal, abnormal not clinically significant or abnormal clinically significant. See [Table 1](#) for assessment time points.

4.6.6. Physical Examination Variables

The physical examination variable values are dichotomized to normal and abnormal. A thorough and complete physical examination will be performed at time points according to visit schedule ([Table 1](#)).

Any abnormal findings during the screening period are recorded as medical history. Any abnormal findings during post-screening period are recorded as adverse events.

4.6.7. Other Safety Variables

Body weight and height will be measured at time points according to [Table 1](#).

Ophthalmological exams: Patients who have a history of certain eye disorders (conjunctivitis, blepharitis, or keratitis) within the last 12 months of the screening visit will be referred during screening to an ophthalmologist (preferably with expertise in treating Cornea and External Eye Disease [‘front-of-the-eye’] subspecialty expert). Patients who experience AESIs related to eye disorders will also be referred to an ophthalmologist (preferably with expertise in treating patients or Cornea and External Eye Disease [‘front-of-the-eye’] subspecialty expert). Further evaluation of these AESIs will be performed including any additional tests, if applicable, as per the discretion of the ophthalmologist.

4.7. Pharmacokinetic Variables

Samples for measurement of functional REGN3500 or total IL-33 (REGN3500 target) will be collected at visits listed in [Table 1](#).

4.8. Immunogenicity Variables

The immunogenicity variables are anti-drug antibody (ADA) status and titer at each time-point/visit. Serum samples for anti-REGN3500 antibody bioanalysis will be collected at time points according to visit schedule (Table 1). In the event a patient sample is positive in the REGN3500 ADA assay at week 16 or the first time point analyzed, the week 4 PK sample may be analyzed in the ADA assay.

Immunogenicity will be characterized by ADA responses and titers observed in patients in the ADA analysis set. ADA responses and titer categories are defined as follows:

- ADA Negative, defined as ADA negative response in the REGN3500 ADA assay at all time points, regardless of any missing samples.
- Pre-existing immunoreactivity, defined as either an ADA positive response in the assay at baseline with all post first dose ADA results negative, OR a positive response at baseline with all post first dose ADA responses less than 9-fold for anti-REGN3500 antibody assay over baseline titer levels
- Treatment-emergent response, defined as a positive response in the ADA assay post first dose when baseline results are negative or missing. The treatment-emergent responses will be further characterized as Persistent, Indeterminate or Transient
 - Persistent Response - Treatment emergent ADA positive response with two or more consecutive ADA positive sampling time points separated by at least 16-week period, for anti-REGN3500 antibody assays, with no ADA negative samples in between
 - Indeterminate Response - as a treatment-emergent response with only the last collected sample positive in the ADA assay
 - Transient Response - a treatment emergent ADA positive assay response that is not considered persistent or indeterminate.
- Treatment-boosted response, defined as a positive response in the ADA assay post first dose that is greater than or equal to 9-fold for anti-REGN3500 antibody assay over baseline titer levels, when baseline results are positive
- Titer categories (Maximum titer values)
 - Low (titer <1,000)
 - Moderate ($1,000 \leq \text{titer} \leq 10,000$)
 - High (titer >10,000)

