5.10. Analysis of Immunogenicity Data

5.10.1. Analysis of ADA Data

The immunogenicity variables described in Section 4.8 will be summarized using descriptive statistics in the ADA analysis set.

The following analysis will be provided based on AAS:

- Number (n) and percent (%) of ADA-negative patients (pre-existing immunoreactivity and ADA negative at all timepoints) in the respective ADA assay by treatment groups
- Number (n) and percent (%) of ADA positive patients (treatment-emergent and treatment-boosted responses) by treatment groups and ADA titer categories
- Number (n) and percent (%) of treatment-emergent ADA-positive patients by treatment group and ADA titer categories
 - a. Number (n) and percent (%) of persistent treatment-emergent ADA-positive patients
 - b. Number (n) and percent (%) of indeterminate treatment-emergent ADA-positive patients

- c. Number (n) and percent (%) of transient treatment-emergent ADA-positive patients
- Number (n) and percent (%) of treatment-boosted ADA-positive patients by treatment groups and ADA titer categories
- Listing of all ADA titer levels will be provided for patients with pre-existing, treatment-emergent and treatment-boosted ADA responses

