Serum REGN3500 Concentration (PK)		X	X	X		X		X		X	X	X	X	X	X	X ¹⁸	X
Anti-REGN3500 Antibody (ADA) ²⁰		X								X					X	X ¹⁸	X

	Screenin g Period ^{13,} 14	Double-Blind Treatment Period									Follow-Up Period						
In-clinic Visit (V) Study Procedure ¹	V1	Baseline V2	V3	V4	V5	V6	V7	V8	V9	EOT V10	V11	V12	V13	V14	EOS V15	Un- sch ¹⁶	ET ¹⁹
Week (W)	-	-	W2	W4	W6	W8	W10	W12	W14	W16	W20	W24	W28	W32	W36	-	-
Day (D)	D-35 to D-1	D1	D15	D29	D43	D57	D71	D85	D99	D113	D141	D169	D197	D225	D253	-	-
Visit Window in Days	-	-	±3	±3	±3	±3	±3	±3	±3	±3	±3	±3	±3	±3	±3	-	-
Biomarkers: ^{1, 11}																	
hs-CRP, SAA	X	X		X		X		X		X				X	X	X	X
TARC	X	X		X		X		X		X				X	X	X	X
Total IgE	X	X		X						X					X	X	X
Total IL-33		X	X	X		X		X		X	X	X	X	X	X	X	X
FBR Samples (serum/plasma)	X	X		X		X		X		X				X	X	X	X
Genomics Sample: ^{1, 11}																	
Whole Blood DNA ¹²		X															
Whole Blood RNA ¹²		X								X					X		X

ADA: anti-drug antibody; BSA: body surface area; D: day; DLQI: Dermatology Life Quality Index; EASI: Eczema Area and Severity Index; ECG: electrocardiogram; e-diary: electronic patient diary; EOS: end-of-study; EOT: end-of-treatment; ET: early termination; FBR: Future Biomedical Research; FSH: follicle-stimulating hormone; GISS: Global Individual Signs Score; HADS: Hospital Anxiety and Depression Scale; HBcAb: hepatitis B core antibody; HBsAg: hepatitis B surface antigen; HCV Ab: hepatitis C virus antibody; HIV Ab: human immunodeficiency virus antibody; hs-CRP: high-sensitivity C-reactive protein; ICF: informed consent form; IGA: Investigator’s Global Assessment; IgE: immunoglobulin E; IL: interleukin; Meds: medications; NRS: Numerical Rating Scale; PK: pharmacokinetic; POEM: Patient Oriented Eczema Measure; SAA: serum amyloid A; SCORAD: SCORing Atopic Dermatitis; TARC: thymus and activation-regulated chemokine (CCL17); V: visit; Unsch: unscheduled visit; W: week; WOCP: women of childbearing potential.

Footnotes for the Schedule of Events Table

1. Assessments/procedures should be conducted in the following order: patient reported outcomes, investigator assessments, safety and laboratory assessments (including sample collection for ADA, PK, biomarkers, DNA, and RNA), and then administration of study drug.
2. Training of patients regarding completion of e-diary to record (1) completion of assessment of Pruritus, Pain, and Sleep Quality NRS scales and (2) emollient usage.

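### SAP 4.8 labels a treatment-emergent ADA response transient when two or more consecutive positives span less than 16 weeks and the last sample is still positive, although no negative result followed

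*SAP*

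**What the plan says.** SAP 4.8 subdivides treatment-emergent responses (positive after the first dose, baseline negative or missing) as follows.

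- **Persistent:** "two or more consecutive ADA positive sampling time points separated by at least 16-week period", and "with no ADA negative samples in between".
- **Indeterminate:** "as a treatment-emergent response with only the last collected sample positive in the ADA assay".
- **Transient:** "Transient Response - a treatment emergent ADA positive assay response that is not considered persistent or indeterminate".

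The schedule in SAP 10.2 (Table 1) places ADA samples at baseline, week 16 (end of treatment, EOT) and week 36 (end of study, EOS). Further samples are taken at an early termination (ET) visit and at unscheduled visits prompted by an adverse event. SAP 4.8 adds that, when the week 16 sample or the first one analysed is positive, "the week 4 PK sample may be analyzed in the ADA assay".

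SAP 5.10.1 reports a count and percentage for each subclass, including "transient treatment-emergent ADA-positive patients", and lists all titers for patients with an ADA response. SAP 5.11.2 lists the ADA categories for the safety association: positive, negative, persistent, and maximum titer level.

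**The concern.** The three definitions do not treat the last sample consistently. Indeterminate covers a response still present when observation ends, but only if exactly one sample was positive. A second consecutive positive less than 16 weeks earlier disqualifies the patient from indeterminate without qualifying for persistent. The remainder rule then assigns transient, although no later negative supports that label.

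The optional re-test shows the problem most clearly. A patient positive only at week 16, with no later sample, is indeterminate. If the laboratory also tests the stored week 4 sample and finds it positive, the same patient becomes transient. Evidence that the antibody was present for longer moves the patient out of the class for unknown duration and into the one whose name suggests a short response. Whether this happens depends on a test that may or may not be run.

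Immunogenicity is a secondary objective (Protocol 2.2, SAP 1.2.2), and the three-way split is a planned output.

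**Working it through.** The plan states no figure here to reproduce. The check applies the SAP 4.8 rules to the sample patterns that the schedule allows.

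**Inputs.** Week 4 = day 29, week 16 = day 113, week 36 = day 253, visit windows ±3 days (SAP 10.2). Persistence threshold: 16 × 7 = 112 days (SAP 4.8). Follow-up after EOT: 20 weeks, including for patients moved to follow-up when the sponsor stopped the study (SAP 2.1). Baseline is taken as negative.

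**Intervals.**
- Week 4 to week 16: 113 − 29 = 84 days (12 weeks). With ±3 days at each end, 78 to 90 days, always below 112.
- Week 16 to week 36: 253 − 113 = 140 days (20 weeks). With windows, 134 to 146 days, always above 112.

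**Classification** (+ positive, − negative):

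| Post-dose pattern | First to last positive | Class as written | Class after the fix |
|---|---|---|---|
| Week 16+, nothing else | single sample | indeterminate | indeterminate |
| Week 4+, week 16+, no later sample | 84 days | **transient** | indeterminate |
| EOT+, then ET+ or AE-visit+ 1 to 15 weeks later, nothing after | 7 to 105 days | **transient** | indeterminate |
| EOT+, then ET+ 16 weeks later | 112 days | persistent | persistent |
| Week 16+, week 36+ | 140 days | persistent | persistent |
| Week 4+, week 16+, week 36+ | 224 days | persistent | persistent |
| Early EOT+ after the sponsor stop, EOS+ 20 weeks later | 140 days | persistent | persistent |
| Week 16−, week 36+ | single positive | indeterminate | indeterminate |
| Week 16+, week 36− | single positive | transient | transient |
| Week 4+, week 16+, week 36− | 84 days | transient | transient |

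The two bold rows are the gap: every sample is positive, yet the class is transient. The 16-week separation can be read as first-to-last positive in a run or as adjacent positives. The bold rows come out the same either way. The reading matters if an extra positive falls between EOT and EOS. Positives at days 113, 183 and 253 are persistent on the first-to-last reading (140 days) but transient on the adjacent reading (70 days each).

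**Size.** No ADA rate is given, nor the frequency of week 4 re-tests, so the number affected cannot be computed. For scale only: 129 patients in five arms is 129 / 5 = 25.8 per arm. If every randomized patient entered the ADA analysis set (an assumption) and the arm were the denominator, one reclassified patient would move a percentage by about 1 / 25.8 = 3.9 points.

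**The case against.** The strongest reply is that the rules work on the scheduled design. With samples at EOT and EOS 20 weeks apart and none in between, two positives are persistent, a positive at EOS alone is indeterminate, and a positive followed by a negative is transient. Sponsor-stopped patients were to have EOT assessments and then the same 20-week follow-up. A patient with one post-dose sample, positive, is indeterminate, which is the likely pattern when one of two scheduled draws is missing. The gap therefore needs an extra positive sample as well as incomplete follow-up. All of this stands and limits the point. It does not remove it: SAP 1.2.4 acknowledges uncollected ADA data, and the re-test, ET and adverse-event samples are all part of the plan.

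A reader might infer three stronger things that the documents do not support.

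- **That these patients are reported as having resolved.** The SAP never says so. It gives transient no meaning beyond not being in the other two classes, still counts the patients as ADA-positive, and lists their titers.
- **That the split is biased towards transient overall.** No net direction can be shown, because the re-test can also work the other way. Positives at week 16 and at an ET visit at week 24 (169 − 113 = 56 days) are transient. Adding a positive week 4 result stretches the run to 169 − 29 = 140 days, which is persistent on the first-to-last reading.
- **That downstream conclusions are affected.** The safety association in SAP 5.11.2 uses neither transient nor indeterminate, the ADA-efficacy analyses were removed (SAP 1.2.4), and all analyses are descriptive. SAP 1.1 says that development in other diseases continues, but not that this split will be used there.

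**Conclusion.** Wrong as written, minor severity. The remainder definition puts a response that was still positive at the last observation into transient whenever two or more consecutive positives, ending with that last sample, span less than 16 weeks. For patients positive only at week 16, the class can also depend on whether an optional re-test is run. Patients with a single positive post-dose sample, and patients positive at both EOT and EOS 20 weeks apart with no sample in between, are classified sensibly and are not part of the problem.

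The effect is confined to the descriptive transient and indeterminate counts in SAP 5.10.1. Overall ADA incidence, titer categories, the persistent count and the SAP 5.11.2 safety categories do not change. The conclusion rests on the literal wording of SAP 4.8 and the sampling days in SAP 10.2. How many patients are affected, if any, cannot be determined from the documents.

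**What to change.** In SAP 4.8, leave Persistent as it is and replace the other two definitions:

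- **Indeterminate:** a treatment-emergent response whose last collected sample is positive and which does not meet the persistence criterion.
- **Transient:** a treatment-emergent response that is not persistent and whose last collected sample is negative.

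The classes stay exclusive and exhaustive, and a positive week 4 re-test can no longer move a patient from indeterminate to transient. One side effect should be accepted knowingly: a positive, negative, positive sequence ending on a positive sample also moves from transient to indeterminate, which is consistent with a response not known to have ended.

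The cost is two sentences in the SAP and a small change to the derivation code. No new samples or assays are needed.
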